8.7 Auxiliary Supply

ProSciento will supply laboratory material necessary for PK and PD sampling, all the safety hematology, biochemistry, and urinalyses (incl. pregnancy test), and for the immunogenicity sampling in collaboration with the laboratories.

9.0 STUDY PLAN

9.1 Study Procedures

9.1.1 Informed Consent and HIPPAA Release

Written informed consent will be obtained from each subject prior to performing any study-specific evaluations. The HIPAA release is embedded in the informed consent document. The informed consent document is subject to review and approval by the Sponsor and will be approved by a qualified IRB. The IRB-approved document must contain, at minimum, the eight basic elements of informed consent set forth in applicable law. Only the most recently IRB-approved informed consent document must be used to consent prospective study subjects. The Investigator (according to applicable regulatory requirements), or a person designated by the Investigator and under the Investigator's responsibility, will fully inform the potential study subject of all pertinent aspects of the Clinical Study, including written information given approval/favorable opinion by the IRB/IEC.

Subjects will be fully informed of their responsibilities and of all the procedures involved in the study, the possible risks, and disadvantages of being dosed with the investigational products, and their rights while participating in the study. They will have the opportunity to ask questions.

Prior to the potential subject's participation in the Clinical Study, the written informed consent form must be signed, name filled in and personally dated by the subject and by the person who conducted the informed consent discussion, and by the Investigator. One copy of the signed and dated informed consent document will be given to the subject and the original retained by the Investigator/CRU.

9.1.2 Screening

Investigators must account for all subjects who sign informed consent forms. The Investigator will keep a Subject Screening and Enrollment Log at the investigational site. Subjects who have screen failed may be allowed to re-screen once at the discretion of the Investigator. A new screening number will be assigned.

Subjects who meet all inclusion criteria and none of the exclusion criteria are eligible for this study and will be invited for the in-house period. Subjects will be instructed on influencing factors, such as refraining from strenuous exercise throughout the entire course of the study, avoidance of alcohol and herbal supplements, caffeinated drinks, smoking or medication and illness/infection as stated in section 7.4.

If subjects are fasting (only water for ≥ 10 hours), all screening assessments may be done on the same day. If subjects are not fasting, they will be invited to return for a second screening visit to complete any missing screening procedures (e.g. laboratory assessments).

9.1.3 Demographics and Medical History

Demographic information and medical history, including smoking status, and medication history will be obtained at Screening.

9.1.4 Physical Examination

The baseline physical examination will consist of the following body systems: (1) eyes; (2) ears, nose, throat, neck, thyroid; (3) cardiovascular system; (4) respiratory system; (5) gastrointestinal system, mouth; (6) dermatologic system; (7) extremities; (8) musculoskeletal system; (9) central and peripheral nervous system and (10) lymph nodes.

An abbreviated physical exam (based on symptoms and including examination of cardiovascular, respiratory, and gastrointestinal system) will be performed by the Investigator (or a qualified physician at the CRU) at time points indicated in the Table 16-1. A complete physical examination may be performed in case the subjects have symptoms or at the discretion of the Investigator.

9.1.5 Height, Weight, and BMI

Height (without shoes) will be measured once, during the Screening visit.

Weight (without shoes) will be measured fasting in the morning, with light clothing and post void at time points indicated in the Table 16-1. The measurement on Day 1 will be taken prior to dosing.

BMI (kg/m2) will be calculated from height and weight.

9.1.6 Vital Signs

Vital signs will include body temperature (*aural*), supine and standing blood pressure (supine BP after 5 minutes resting, standing BP within 3 minutes in upright position), respiration rate and pulse rate (after 5 minutes resting). Vital sign measurements will be performed at days indicated in the Table 16-1.

Body temperature: Assessments will be performed once daily, as stated in the Table 16-1. Measurements may be taken more frequently, if deemed necessary by the Investigator. Measurement on Day -1 will be performed as baseline assessment. Measurements will continue throughout the study. Timepoints must not interfere with ABPM measurements.

Blood pressure:

Supine and standing assessments will be performed. Measurements will be taken once at Screening and once on Day -2 and twice (morning and evening) on Day -1. The rest of the measurements will follow the following sampling schedule: On Day 1, measurements will be performed pre-dose and at 4, 8 and 12 hours post-dose. On Day 2 at 24 and 36 hours, on Day 3 at 48 hours, on Day 4 at 72 hours, on Day 5 at 96 hours, on Day 6 at 120 hours, on Day 7 at 144 hours post-dose with a sampling window of \pm 15 min for each timepoint. Additional measurements will be taken on Day 10 at 216 hours (\pm 1 day), on Day 17 at 384 hours (\pm 1 day), and on Day 30 at 696 hours (\pm 2 days) post-dose.

Measurements will be performed on the arm that is not connected to the ABPM system. Timepoints must not interfere with the ABPM measurements.

Pulse rate and respiration rate: Assessments will be performed as stated in the Table 16-1 at timepoints for blood pressure measurements. Pulse rate will be assessed in combination with both, supine and standing blood pressure measurements. Respiratory rate will be assessed at timepoints of supine blood pressure measurements.

9.1.7 Concomitant Illness and Therapy

Concomitant therapy is any medication given in addition to the investigational product (including over-the-counter medications, herbal medications, and vitamin supplements) administered between screening and follow-up.

Concomitant illness is any significant medical condition or disease that is present at study start (signing of informed consent). This includes clinically significant laboratory, electrocardiogram (ECG), or physical examination abnormalities noted at Screening examination

Details of all concomitant illnesses and therapies must be recorded at study entry and must be recorded on the subject's CRF. Any changes in concomitant medication must be recorded at each visit. If the change influences the subject's eligibility to continue in the study, the Sponsor must be informed. The information collected for each concomitant medication includes, at a minimum, start date, stop date or continuing, and indication.

AEs related to administration of these therapies or procedures must also be documented on the appropriate CRF.

9.1.8 Procedures for Clinical Laboratory Samples

All samples will be collected in accordance with acceptable laboratory procedures. Laboratory samples (Table 9-1) will be taken as described in the Schedule of Events.

Table 9-1 Clinical Laboratory Assessments

Hematology	Serum Chemistry	Urinalysis
CBC with differential:	Hepatic function panel:	Routine urinalysis with
Hematocrit	Alanine aminotransferase	microscopic examination on
Hemoglobin	(ALT/SGPT)	positives(a):
mean corpuscular volume	alkaline phosphatase, serum	Color
(MCV)	aspartate aminotransferase	appearance,
mean corpuscular hemoglobin	(AST/SGOT)	specific gravity
(MCH)	bilirubin, direct	pН
mean corpuscular hemoglobin	bilirubin, total	protein
concentration (MCHC)	protein, total, serum	glucose
red cell distribution width	•	ketones
(RDW)	Renal function panel:	occult blood
percentage and absolute	Albumin, serum	leukocyte esterase
differential counts	BUN	nitrite
platelet count	BUN: creatinine ratio	bilirubin

red cell count (RBC) white blood cell count (WBC)	calcium, serum urobilinogen carbon dioxide, total chloride, serum creatinine, serum glucose, serum phosphorus, serum potassium, serum sodium, serum						
	Lipid panel: Cholesterol, total high-density lipoprotein (HDL) cholesterol low-density lipoprotein (LDL) cholesterol (calculated) triglycerides very low-density lipoprotein (VLDL) cholesterol (calculated)						
	Additional parameters: Amylase Lipase Calcitonin Lactic acid dehydrogenase (LDH) Gamma-Glutamyl Transferase Magnesium Uric Acid						

Diagnostic Screening

Serum/Plasma/Whole Blood	Urine	Breath
HBsAg	Drug Screen Profile	Alcohol breath test at
Anti-HCV	Amphetamines	timepoints stated in the SOE
HIV 1/2	Barbiturates	at the CRU
TSH(b)	Benzodiazepines	
PTT	cocaine (as benzoylecgonine)	
PT	methylenedioxymetamphetamines	
INR	opiates	
HbA1c	Oxycodon	
	phencyclidine (PCP)	
	propoxyphene (Darvon®)	
	tricyclic anti-depressants	
	Urine drug screen as stated in the	
	SOE via commercial kit at the	
	CRU.	
	Female Subjects Only	

Free fatty acid (FFA) C-reactive protein (CRP)

human chorionic gonadotropin (hCG)performed at Screening. Follicle-stimulating hormone (FSH) test for postmenopausal women (defined as amenorrheic female subjects <60 years of age and not surgically sterile) at Screening. Urine pregnancy testing via commercial kit at CRU will be performed at timepoints stated in the Schedule of Events. Urine pregnancy testing may be performed per Investigator's discretion at additional timepoints during the study, if there is reason to believe the subject might be pregnant.

- (a) Microscopic analysis should be performed only if urine evaluations are abnormal.
- (b) In the event of abnormal TSH, Free T3/T4 may be collected at Investigator discretion.

The local laboratory will perform all necessary laboratory tests listed above. The results of laboratory tests will be sent to the Investigator or designee, who is responsible for reviewing these results. All laboratory safety data will be faxed or transferred electronically.

Laboratory reports must be signed and dated by the Investigator or designee indicating that the report has been reviewed and any abnormalities have been assessed for clinical significance.

All clinically significant laboratory abnormalities must be recorded as an AE. A clinically significant laboratory abnormality may be verified by retesting and may be followed upon discretion of the Investigator.

9.1.9 Contraception

Females must be non-pregnant and non-lactating, and either surgically sterile (eg, tubal occlusion, hysterectomy, bilateral salpingectomy, bilateral oophorectomy) or postmenopausal for >12 months. The site will make an effort to retrieve medical records to document the sterility, however, the absence of records will not exclude the subject. In case that medical records cannot be obtained, serum pregnancy testing will be conducted at Screening, and urine pregnancy testing will be conducted throughout the study. Postmenopausal status will be confirmed through testing of FSH levels ≥ 25.8 mIU/mL at screening for amenorrheic female subjects <60 years of age. Female subjects who state they are postmenopausal at the screening visit but have a FSH value < 25.8 mIU/mL, may have a serum hCG pregnancy test performed on a separate day. If test is negative

and the subject agrees to be on a highly effective contraceptive method, subject may be enrolled in the study at the discretion of the Investigator.

Female subjects of child-bearing potential must use highly effective contraceptive methods., Highly effective contraceptive methods are considered those with failure rate less than 1% undesired pregnancies per year, including hormonal intrauterine devices (coil), oral hormonal contraceptives, sexual abstinence, or a surgically sterilized partner. Oral hormonal contraceptives have to be taken at least 2 months prior to Screening until 30 days after the last Follow-up Visit.

During the course of the study, regular serum human chorionic gonadotropin (hCG) pregnancy tests will be performed for sterilized women, when medical records are not available. In addition to a negative serum hCG pregnancy test at Screening, subjects also must have a negative urine hCG pregnancy test at check-in to in-house periods.

Males must be surgically sterile (at least 1-year post vasectomy), abstinent or if engaged in sexual relations of child-bearing potential, the subject and his partner must be using an acceptable contraceptive method from screening and for a period of 30 days after the last Follow-up visit. Acceptable methods of contraception are the use of condoms together with spermicidal foam/gel/film/cream/suppository. In addition, they must be advised not to donate sperm during this period. Male subjects must also encourage their female partner to use effective contraception. Effective contraceptive for the female partner includes surgical sterilization (e.g., bilateral tubal ligation, bilateral salpingectomy, bilateral oophorectomy), hormonal contraception, intrauterine contraception/device, or barrier methods (female condom, diaphragm, sponge, cervical cap) together with spermicidal foam/gel/film/cream/ suppository. The adequacy of other methods of contraception will be assessed on a case-by-case basis by the Principal Investigator.

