	Starting dose is determined with 0.01 mg/kg for Cohort 1. The maximum human dose is determined by the exposure seen at the NOAEL in the 4-week toxicology study in the rat which corresponds to approximately 0.16 mg/kg in a human according to PK prediction. Doses between cohorts will not exceed a 2-fold increase relative to the specified doses stated above. Dose escalation will be determined in safety review and dose escalation meeting by Sponsor and Investigator and will be based on clinical safety and available PK data.		
Route of Administration	All study drugs will be administered by SC injection into the abdominal wall.		
Duration of Participation	The duration of participation in this study, including Screening, Treatment and Follow-up will be approximately 9 weeks for each subject.		
Inclusion Criteria	Subjects who meet all criteria at Screening will be included in the study:		
	1. Male and	female subjects.	

- 2. Age \geq 18 to \leq 65 years.
- 3. Body mass index (BMI) \geq 30 to \leq 40 kg/m², with stable body weight by history for 3 months (defined as change < 5%).
- 4. HbA1c < 6.5 %.
- 5. Female subjects must be non-pregnant and non-lactating. Females of child bearing potential must use highly effective contraceptive methods, stable at least 2 months prior to the screening. Male subjects must be surgically sterile, abstinent or if engaged in sexual relations of child-bearing potential, the subject and his partner must use an acceptable method of contraception.
- 6. Ability to provide written informed consent.

Exclusion Criteria

Subjects who meet any of the following criteria will be excluded from the study:

- Previous surgical treatment for obesity (bariatric surgery, gastric banding, etc.) or any other gastrointestinal surgery that may induce malabsorption, history of bowel resection > 20 cm, any malabsorption disorder, severe gastroparesis, any GI procedure for weight loss (including LAP-BAND®), as well as clinically significant gastrointestinal disorders (e.g. peptic ulcers, severe GERD) at Screening.
- 2. Use of antacids, anticoagulants, drugs that directly modify gastrointestinal (GI) motility, including, but not limited to, anticholinergics, antispasmodics, 5HT3 antagonists, dopamine antagonists, or opiates within 2 weeks of screening.

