The toxicity studies of HM15211, repeat dose toxicity up to 4 weeks in rats and monkeys, and in vitro genotoxicity studies, were conducted. Local tolerance of HM15211 was investigated in 4-week repeated rat and monkey studies. Additional studies were conducted with HMC001 (inactive ingredient) in rat and monkey up to 4 weeks repeat dose toxicity studies.

No target organ was identified during the 4 weeks repeat dose toxicity studies of HM15211. All changes were completely or partially reversible during the recovery period.

The majority of findings were related to fasting effect or pharmacological effect of glucagon. No adverse test article-related findings at the injection sites were noted. No adverse events were observed in HMC001 studies.

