6.2 Study Description

Each subject will undergo the following procedures during the study:

Screening Visit:

Before the screening takes place, potential subjects for the trial will be provided with written and oral information about the trial and the procedures involved. Subjects must sign the informed consent form (ICF) prior to entering the study. Please see section 9.1.1 for further details.

The screening visit will be performed up to 28 days prior to the first dosing day, to identify eligible subjects for the study. All assessments performed at the screening visit are stated in Table 16-1 and will be recorded in the electronic case report form (eCRF). Please see section 9.1.2 and 11.2 for further details.

In-house Period:

Subjects will check in to the clinical research unit (CRU) in the morning of Day -2 for a 9-day in-house period. They will receive standardized meals throughout their in-house stay. A 12-lead standard ECG will be performed. Subjects will be connected to an ABPM system for measurement of blood pressure (BP), and measurements will be started overnight on Day -2 to familiarize the subjects with the device. Measurements will continue until the morning of Day 4.

In the morning of Day -1, subjects will get connected to a Holter ECG for continued measurement of the heart rate activity until the morning of Day 4.

Only 24-hour monitoring data from Day -1 to Day 1 will be used for the monitoring evaluation as baseline assessments for ABPM and Holter ECG monitoring. For measuring timepoints, please see sections 9.1.14 and 9.1.15.

Subjects will be randomized to a single SC injection of HM15211 or placebo. Randomization will take place as close to the drug administration as possible.

On Day 1, after an \geq 10 h overnight fast, subjects will be dosed with HM15211or placebo at approximately 08:00 hours (t=0), through SC injection into the abdominal wall by qualified study staff. Measurements of vital signs, ECG, blood sampling for PK and PD analyses, local injection site evaluation, and laboratory parameter will be performed for safety evaluation, at timepoints stated in Table 16-1.

ABPM and Holter ECG monitoring will be continued until the morning of Day 4 for the post-dose evaluation. 24-hour monitoring evaluations will be performed together with available PK data, in order to determine the best time period for 24-h monitoring period around PK_{peak}.

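### Section 9.1.9 lets a woman with unconfirmed menopause enrol on an undertaking to use contraception, inclusion criterion 5 demands 2 months of stable use before screening, and the protocol does not say which governs

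*Protocol*

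**What the plan says.** - **Protocol 9.1.9, FSH route.** An FSH of at least 25.8 mIU/mL confirms menopause in amenorrheic women under 60. A woman who reports being postmenopausal but falls below that value "may have a serum hCG pregnancy test performed on a separate day". If it is negative and "the subject agrees to be on a highly effective contraceptive method, subject may be enrolled in the study", entry is left to the Investigator's discretion. No length of prior use and no start date are given.
- **Inclusion criterion 5 (synopsis and section 7.1).** "Females of child bearing potential must use highly effective contraceptive methods, stable at least 2 months prior to the screening". It contains no exception.
- **Protocol 9.1.9, next paragraph.** "Oral hormonal contraceptives have to be taken at least 2 months prior to Screening". The 2-month rule is repeated there for this one class of method only.
- **Protocol 9.1.2.** Eligibility depends on meeting all inclusion criteria. It adds: "Subjects who have screen failed may be allowed to re-screen once at the discretion of the Investigator".
- **Protocol 6.2.** "The screening visit will be performed up to 28 days prior to the first dosing day".
- **Pregnancy testing (9.1.9, 7.4, Table 16-1).** There is a serum test at Screening and a urine test at check-in on Day -2. A positive urine test bars check-in.

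**The concern.** The FSH route handles a woman whose menopause the screening test failed to confirm. By asking her for an hCG test and for contraception, 9.1.9 itself treats her as possibly fertile. Its contraceptive condition, however, looks forward, whereas criterion 5 looks back 2 months from screening. A site reading 9.1.9 could enrol a woman whom criterion 5 excludes.

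What is at stake is fetal exposure in a first-in-human study. Section 4.3 summarises the toxicology as follows: "repeat dose toxicity up to 4 weeks in rats and monkeys, and in vitro genotoxicity studies, were conducted". No reproductive study appears in that summary; the Investigator's Brochure, to which the protocol refers for detail, is not at hand. Protection therefore rests on contraception and pregnancy testing. The drug is given as a single dose, so the withdrawal rule in 9.1.10 cannot undo an exposure that has already happened.

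**Working it through.** The plan states no figure to reproduce. The check is a comparison of texts plus simple timing.

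**1. The two rules side by side**

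| | Criterion 5 (synopsis, 7.1) | FSH route (9.1.9) |
|---|---|---|
| Who | Women of child-bearing potential (term not defined) | Self-reported postmenopausal, FSH < 25.8 mIU/mL |
| Contraception | Highly effective, stable ≥ 2 months before screening | Undertaking to use a highly effective method |
| Start date | Implied by the 2 months | None |
| Other conditions | All other criteria (9.1.2) | Negative separate-day serum hCG, Investigator's discretion |

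Neither text refers to the other.

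**2. Timing.** Let screening fall *d* days before the dose, with *d* ≤ 28 (6.2). Assume 2 months is about 60 days.

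- Criterion 5: at least 60 days of use at screening, so at least 60 + *d* at dosing. With *d* = 28 this is 60 + 28 = 88 days.
- A woman who starts because of her FSH result: 0 days at screening and at most *d* at dosing. With *d* = 28 this is at most 28 days. It can be as little as 0, because no start date is set.

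Since 0 < 60 at screening whatever *d* is, she cannot satisfy criterion 5 in the same screening period. She could do so only by re-screening, which 9.1.9 does not ask for.

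**3. Which women are affected.** The methods named in 9.1.9 are hormonal intrauterine devices, oral hormonal contraceptives, abstinence and a sterilised partner. A newly started oral contraceptive already fails the 2-month rule in the next paragraph. A woman with long-standing abstinence, a sterilised partner or an established device already meets criterion 5. What remains is the woman who newly starts a non-oral method.

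**4. What the tests leave open.** Three tests precede the dose: serum at Screening, serum on a separate day, and urine on Day -2. They detect an established pregnancy but may miss a very recent conception. The documents give no figure for that window; assume the last 7 to 14 days before Day -2. Table 16-1 has no Day 0, so Day -2 is 2 days before dosing on Day 1. The window therefore opens 2 + 7 = 9 to 2 + 14 = 16 days before the dose.

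- Start promptly after screening at *d* = 28: the window is covered.
- Screening interval below about 9 to 16 days, or a method started that late: part or all of the window is not covered.

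Subjects are in-house from Day -2 to Day 7, so the days immediately around dosing add little.

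**The case against.** The strongest reply is that there is no true contradiction. Section 9.1.9 does not claim to waive criterion 5, its wording is permissive, and 9.1.2 still requires all inclusion criteria. On a strict reading a new starter of child-bearing potential is simply screened out. Alternatively, since child-bearing potential is not defined and she reports being postmenopausal, criterion 5 may not reach her, and the FSH sentence is a specific rule for an unconfirmed group.

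This stands in part. It is right that 9.1.9 does not openly override criterion 5, so a reader who infers that the protocol definitely admits ineligible women goes too far. But the first reading empties the FSH sentence of effect for every new starter, although that sentence looks forward. The second leaves a possibly fertile woman with no prior-use rule unless she takes an oral contraceptive. The protocol does not choose between them.

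The reply is also right about safeguards. A reader might infer that one serum hCG is all that stands between such a woman and dosing. It is not: the Screening serum test, the Day -2 urine test and the Investigator's judgement apply too. None of these supplies prior contraception, and no standard is stated for the discretion.

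**Conclusion.** The inconsistency is real and worth correcting, but it is narrow. It affects only women with unconfirmed menopause who newly start a non-oral method. Their number is not given and is probably small. For them, the 2 months of prior use that criterion 5 demands cannot be met within a screening window of at most 28 days, yet 9.1.9 offers a way in. The residual risk is a very recent conception missed by the tests when the screening interval is short or the method starts late; its width rests on the assumed 7 to 14 days. Sample size and analysis are not affected.

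Two stronger inferences are not supported:

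- The gap of about 60 days between the two rules might be read as a measure of pregnancy risk. It only restates the 2-month rule. On the assumption above, a prompt start after screening at Day -28 already covers the window that matters.
- Table 9-1 describes the FSH-tested group as "defined as amenorrheic female subjects <60 years of age and not surgically sterile", with no minimum duration of amenorrhea, which might suggest that the route is open to women far from menopause. Section 9.1.9 opens with a requirement of more than 12 months postmenopausal, and the route covers women who report that status, so the table cannot carry that reading.

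**What to change.** Amend the FSH sentence in 9.1.9 to say that a woman who reports being postmenopausal but has FSH below 25.8 mIU/mL is treated as of child-bearing potential and may enrol only if she meets inclusion criterion 5. The existing negative separate-day serum hCG and Investigator's discretion stay in place. If she does not meet criterion 5, she is a screen failure and may use the single re-screen in 9.1.2 once she has 2 months of stable use.

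The cost is one sentence. A few women will be delayed by about 2 months or not enrolled. Women already on a stable method are unaffected, no procedure is added, and sample size and analysis do not change.
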